5.4 Baseline Evaluation

Baseline information will be collected for each Subject to assess the presence of neurological symptoms potentially related to the AVM. The presence and history of any significant medical illnesses and any symptoms related to the AVM will also be collected. For additional assessments that will be performed at baseline, please refer to Table 1.

5.4.1 Imaging

A review of images of the AVM at baseline will be completed to confirm the diagnosis of a brain AVM. Baseline imaging will be conducted no earlier than 1 month prior to the embolization procedure.

5.4.2 Concomitant Medications

All medications that a patient is taking starting 30 days prior to screening will be collected and followed for the duration of the study. In addition, the following medications will be collected throughout the study: antithrombotic, antiplatelet, anticoagulant, all medications administered during the study procedure, and medications associated with adverse events.

5.5 Screen Failure

Subject will be considered a screen failure if:

- The Subject signs the ICF but fails to meet study inclusion/exclusion criteria during the screening and baseline phase.
- The Subject signs the ICF, meets the study inclusion/exclusion criteria but an attempt to use the Apollo™ micro catheter is not performed.

5.6 Enrollment

A Subject will be considered enrolled once the Apollo™ micro catheter is advanced inside the blood stream of the Subject.

5.7 Pre-Embolization

Neurological functioning will be assessed using the mRS, NIHSS, and Barthel Index. Pre-embolization imaging will also be collected.

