3 STUDY OBJECTIVES

3.1 Primary Composite Endpoint (30 days)

- Incidence of catheter-related AEs per Subject:
 - Premature (unintentional) catheter tip detachment with clinical sequelae*
 - Catheter rupture/break/fracture with clinical sequelae*, and
 - Retained catheter body in the vasculature.

*Clinical sequelae are defined as all focal neurologic deficits related to lesions within the vascular territory catheterized. Vascular territory catheterized is defined as the brain tissue supplied by the vascular tree selectively catheterized using the Apollo™ micro catheter.

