5.3.1 Schedule of Assessments

An overview of the assessments to be performed is provided in Table 1.

Table 1. Schedule of Assessments

Assessment	Baseline (-30 days)	Pre- Embolization	Embolization Procedure	Post- Embolization Discharge or +24 hours post- embolization	Surgical Resection	30 Day Follow-up ¹ (+/-7 days)	12 Month Follow-up ² (+/-42 days)
Informed Consent	♦						
Inclusion/Exclusion	♦						
Demographic Characteristics	♦						
Medical History	♦						
Brain AVM characteristics	♦						
Physical Exam	♦						
Neurologic Exam	♦						
Barthel Index		♦		♦		♦	♦
Modified Rankin Scale (mRS)		♦		♦		♦	♦
National Institutes of Health Stroke Scale (NIHSS)		♦		♦		♦	♦
Imaging	•	♦	♦	♦	♦	♦ ³	♦
Embolization Procedure Information and Device Usage or Surgical Resection			♦	♦	♦		
Technical Events			♦				
Concomitant Medications	•	♦	♦	♦	♦	♦	♦
Adverse Events			♦	♦	♦	♦	♦

1. 30 day follow-up will occur 30 days after surgical resection, or 30 days after initial embolization if resection is not done.

2. Only for Subjects with catheter and/or catheter tip retention. If the Subject has had multiple embolization procedures, the 12-month visit will take place 12 months after the initial embolization procedure.

3. Subjects with catheter and/or catheter tip retention, or based on physician assessment.

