5.8 Embolization Procedure

Embolization with Onyx™ 18 LES or Onyx™ 34 LES will be performed in a neuroangiography suite using customary endovascular techniques. Intravenous sedation or general anesthesia will be used to assure Subject comfort and safety. Additional safety measures such as neurophysiological monitoring, or similar practice standards are permitted. Subjects will be heparinized, per the institutional protocol, after placement of an arterial sheath. The anticoagulation regimen and all medications used will be recorded.

The intended use of the study device and components are outlined in the IFU. Any additional pre-operative imaging and neurologic exams performed will be collected to assess changes since baseline. Table 1 describes a list of assessments that will be performed at this visit. For Subjects undergoing staged embolization procedures, data from each embolization procedure will be captured in the study electronic case report forms (eCRFs).

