5.9 Post-Embolization Discharge

All Subjects will undergo a discharge assessment to evaluate neurological functioning after the embolization procedure. Table 1 describes a list of assessments that will be performed at this time point.

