5.11 Follow-up Evaluations

5.11.1 30-Day

Subject who underwent surgical resection will complete a 30-day visit 30 days after surgical resection. For Subjects not undergoing surgical resection, the 30 day visit will be performed 30 days after the initial study embolization. Table 1 describes a list of assessments that will be performed at this visit. Subjects with a retained catheter/tip will undergo imaging at this time point. Subjects experiencing AEs may undergo imaging per physician discretion. Subjects not experiencing an AE and in whom no part of the catheter was retained will complete the study. Subjects experiencing an AE and in whom no part of the catheter was retained will continue to be followed up until AE resolution.

5.11.2 12-Month

Subjects in whom a catheter and/or tip were retained will have a 12-month study visit. If the Subject has had multiple embolization procedures, the 12-month visit will take place 12 months after the initial embolization procedure. If the Subject is experiencing ongoing AEs at 12 months, the Subject will be followed until resolution of the AE. The clock will only reset, if during re-treatment the catheter tip detaches in a non-target location and is not resected. Final imaging will be required at this visit. Table 1 describes a list of assessments that will be performed at this visit.

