9.2.3 Analysis Baseline Demographics and Procedural Characteristics

Descriptive statistics will be generated for pre-intervention demographics, procedural characteristics, and follow-up data collected. Categorical variables will be analyzed using

frequency, incidence, and event rate. For continuous variables collected in the study, analysis will include mean, median, standard deviation, and range.

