9.2.4 Analysis of Primary Endpoint

The primary endpoint is the composite of any of the following catheter related adverse events:

- Premature (unintentional) catheter tip detachment with clinical sequelae
- Catheter rupture/break/fracture with clinical sequelae
- Retained catheter body in the vasculature

The primary analysis for the primary endpoint is based on Subject counts, not event counts. A Subject with more than one event will be counted only once toward the event rate based on the total number of Subjects with adverse events. An event rate based on event counts will also be presented. For example, if a Subject experiences one "Premature (unintentional) catheter tip detachment with clinical sequelae" and one "Retained catheter body in the vasculature", the Subject will be counted once in the rate of total Subjects with primary endpoint; the same Subject will be counted once in the individual event category of "Premature (unintentional) catheter tip detachment with clinical sequelae" and once in the "Retained catheter body in the vasculature" category.

The primary endpoint will be summarized as the event rate per Subject with a one-sided 95% upper confidence bound using the Exact method. The upper bound will be compared to the performance goal of 9.6%. If this upper bound is less than 9.6%, it is considered that the Apollo™ micro catheter meets the primary objective.

One interim analysis is planned for this study. An interim assessment will be performed when 80 subjects have reached the 30-day follow-up. If the one-sided 96% upper confidence bound is below the pre-specified threshold of 9.6%, the primary safety objective is considered to be met and early trial stop for success will be claimed. On those subjects already enrolled, follow-up will continue according to the protocol. Otherwise, the trial will continue and the final analysis will be performed at the end of study. The 96% confidence level is used for the interim analysis to ensure the overall type I error is controlled at the 0.05 level. In addition, the conditional power will be calculated at the interim analysis to determine if a sample size adjustment is necessary. It will not be necessary to adjust the alpha level if the conditional power is greater than 50% (Chen et al., 2004). However, in case that the conditional power is below 50%, the procedure of Cui et al. (1999) will be followed to ensure the study-wise type I error rate is well controlled.

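### NIHSS, mRS and Barthel are scored before and after embolization, but no within-Subject comparison is planned and a recorded NIHSS rise reaches the Clinical Events Committee only if the investigator enters an AE

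*Combined protocol and SAP*

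**What the plan says.** - **Scales.** Section 5.7: "Neurological functioning will be assessed using the mRS, NIHSS, and Barthel Index". Table 1 (section 5.3.1) marks all three before embolization, at discharge or 24 hours, at 30 days, and at 12 months for Subjects with a retained catheter or tip. Section 5.9 adds: "All Subjects will undergo a discharge assessment to evaluate neurological functioning after the embolization procedure".
- **Analysis.** Section 9 does not name any of the three scales. Section 9.2.3 says: "Descriptive statistics will be generated for pre-intervention demographics, procedural characteristics, and follow-up data collected". Section 9.2.1 adds frequency distributions, cross tabulations and Subject listings in general terms. There is no change score, shift table or definition of worsening. The only mention of change is in section 5.8, and it concerns extra pre-operative examinations: "Any additional pre-operative imaging and neurologic exams performed will be collected to assess changes since baseline".
- **Primary endpoint.** Premature tip detachment and catheter rupture, break or fracture count only with clinical sequelae. Section 3.1: "Clinical sequelae are defined as all focal neurologic deficits related to lesions within the vascular territory catheterized". No scale, threshold or reference status is given. The third component, "Retained catheter body in the vasculature", needs no deficit.
- **Route to adjudication.** Section 6 collects all AEs with a neurological cause, and section 8.1 has the committee review and adjudicate study AEs. Section 5.11.1: "Subjects not experiencing an AE and in whom no part of the catheter was retained will complete the study".

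**The concern.** The protocol itself notes that AVM patients present with hemorrhage, seizures or progressive deficit (section 1.2.1), and section 5.4 records neurological symptoms already present at baseline. A mean or median NIHSS at 30 days therefore mixes old deficits with new ones, although each Subject's own reference score has been recorded. For a safety study the informative quantity is worsening from that score.

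The second issue is ascertainment. For two primary components, whether an event counts depends on whether a deficit is recognised. The plan relies on the investigator entering it as an AE. A Subject could have a catheter break and a higher NIHSS at discharge, with both on file, and no stated rule would bring the two together. An event missed in this way lowers the observed rate, and the success rule has a margin of one event.

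**Working it through.** **1. Reproduce the plan's figure.** Section 9.1 states that 5.6% at N = 161 gives an upper bound of 9.6%. The one-sided exact bound is the 0.95 quantile of Beta(x+1, n−x).

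- 9/161 = 5.59%, bound 9.55%, which rounds to the stated 9.6% and passes.
- 10/161 = 6.21%, bound 10.31%, which fails.

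The final test therefore passes with 9 or fewer events, and one event can decide it.

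**2. Interim rule (section 9.2.4).** With 80 Subjects and a 96% one-sided bound, 2/80 gives 8.01% (pass) and 3/80 gives 9.79% (continue).

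**3. Chance of passing at observed rate q.**

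P(pass) = P(X₁ ≤ 2 | 80, q) + Σ over x₁ = 3 to 9 of P(X₁ = x₁ | 80, q) × P(X₂ ≤ 9 − x₁ | 81, q)

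At q = 9.6% with nothing missed: 1.41% + 4.08% = 5.5%.

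**4. Missed events.** Let s be the share of composite events that depend on sequelae, and m the fraction of those that is missed. Then q = 9.6% × (1 − s·m). The documents give neither s nor m, so the values below are assumptions.

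| s | m | q | Chance of passing |
|---|---|---|---|
| any | 0 | 9.60% | 5.5% |
| 25% | 10% | 9.36% | 6.6% |
| 25% | 20% | 9.12% | 7.9% |
| 50% | 10% | 9.12% | 7.9% |
| 50% | 20% | 8.64% | 11.3% |

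If s = 0 (every event is a retained catheter body) or m = 0, nothing changes.

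**5. Which Subjects a score check should cover.** Section 9.2.6 expects 50% to 80% of Subjects to have the tip retained by design: 0.50 × 161 ≈ 80 to 0.80 × 161 ≈ 129. A check triggered by any tip detachment would screen most of the study for an event that is not a primary component. Limiting it to premature detachment and rupture, break or fracture matches the endpoint.

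**6. Timing.** Under section 5.11.1 the 30-day visit of a resected Subject falls 30 days after surgery. A rise at that visit may be surgical, so resected and non-resected Subjects have to be shown separately. Section 5.8 allows staged procedures, so the reference score has to be named.

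**The case against.** The strongest reply is that deficits already have a route. A new deficit meets the AE definition in section 6.1. Section 6 collects neurological AEs whatever their seriousness and requires their location relative to the catheterized territory. The committee can request source documents and imaging (section 8.1), eCRF entries are verified against medical records (section 11), and investigators who fail to report AEs may be terminated (section 13.2). Nothing bars anyone from using an NIHSS rise as evidence. Cross tabulations and listings are within the stated methods, and edit checks may sit in a data management plan that is not part of these documents.

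Most of this stands, and it rules out three stronger readings that a reader might infer:

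- *That new deficits are missed.* The documents show only that they may be: reporting is required, and only the score-based backstop is absent.
- *That the primary rate is biased downward overall.* The sequelae definition does not require the deficit to be new, so a pre-existing deficit could be counted and push the rate up. Mixing of old and new deficits applies to the score summaries, not to the primary rate.
- *That missing 20% of all composite events, which gives a 21.4% chance of passing, is a fair illustration.* It would require every event to depend on sequelae; a retained catheter body does not.

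The reply does not supply a planned paired comparison, or a stated path to the committee for a rise that was not entered as an AE. Section 8.1 gives the committee AEs, not scores. The glossary also defines study AEs as SAEs and device- or procedure-related events, leaving out the neurological category that section 6 lists.

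**Conclusion.** The gap is real but moderate. The plan collects paired neurological scores, specifies no paired analysis of them, and has no stated score-based check on the deficits that two primary components require. By assumption only, the chance of passing at a true 9.6% rises from 5.5% to about 6.6-11.3%, for a sequelae-dependent share of 25-50% with 10-20% of those missed.

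The calculation assumes that all 161 Subjects are in the Full Analysis Set, that the sample size is not changed at the interim, and that no pre-existing deficit is counted in error. With about 140 evaluable Subjects after the planned 13% attrition (161 × 0.87 = 140), and looking at the final test only, the starting figure is 3.6% rather than 5.5%. The documents cannot show how often a deficit would go unreported. The change is worth making because it is cheap and the success rule turns on one event.

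**What to change.** 1. **Section 9.2.6, new table.** Report the number and percentage of Subjects whose NIHSS and mRS have worsened from the last pre-embolization score, at discharge or 24 hours and at 30 days, with exact 95% intervals and the paired change. For staged procedures, use the score taken before the relevant procedure, and confirm that the scales are recorded before each one. At 30 days, show resected and non-resected Subjects separately.
2. **Score-triggered review (sections 8.1 and 9.2.4).** In any Subject with a premature (unintentional) tip detachment or a catheter rupture, break or fracture, an NIHSS above that reference score at discharge or 30 days opens a query. The case goes to the committee to judge clinical sequelae, whether or not an AE was entered.

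The committee still decides cause, so a rise due to resection or intended occlusion is not counted automatically. The cost is one table, one database check and a few extra committee reviews, with no new visits. If the data management plan already contains such a check, citing it in the protocol would cover the query step; the referral to the committee would still need to be stated.

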5.8 Embolization Procedure

Embolization with Onyx™ 18 LES or Onyx™ 34 LES will be performed in a neuroangiography suite using customary endovascular techniques. Intravenous sedation or general anesthesia will be used to assure Subject comfort and safety. Additional safety measures such as neurophysiological monitoring, or similar practice standards are permitted. Subjects will be heparinized, per the institutional protocol, after placement of an arterial sheath. The anticoagulation regimen and all medications used will be recorded.

The intended use of the study device and components are outlined in the IFU. Any additional pre-operative imaging and neurologic exams performed will be collected to assess changes since baseline. Table 1 describes a list of assessments that will be performed at this visit. For Subjects undergoing staged embolization procedures, data from each embolization procedure will be captured in the study electronic case report forms (eCRFs).

5.8.1 Device Use

Detailed information on devices used during the procedure will be collected for the following:

- Ancillary devices
- DMSO
- Onyx™ LES
- Apollo™ micro catheter

5.9 Post-Embolization Discharge

All Subjects will undergo a discharge assessment to evaluate neurological functioning after the embolization procedure. Table 1 describes a list of assessments that will be performed at this time point.

5.10 Surgical Resection

Some Subjects may undergo complete or partial surgical resection of their AVM. Information about the surgical resection procedure, imaging, concomitant medications, and AEs as defined in Section 6.1 will be collected (see Table 1). Data regarding the degree of resection and catheter retainment will be captured.

5.11 Follow-up Evaluations

5.11.1 30-Day

Subject who underwent surgical resection will complete a 30-day visit 30 days after surgical resection. For Subjects not undergoing surgical resection, the 30 day visit will be performed 30 days after the initial study embolization. Table 1 describes a list of assessments that will be performed at this visit. Subjects with a retained catheter/tip will undergo imaging at this time point. Subjects experiencing AEs may undergo imaging per physician discretion. Subjects not experiencing an AE and in whom no part of the catheter was retained will complete the study. Subjects experiencing an AE and in whom no part of the catheter was retained will continue to be followed up until AE resolution.

5.11.2 12-Month

Subjects in whom a catheter and/or tip were retained will have a 12-month study visit. If the Subject has had multiple embolization procedures, the 12-month visit will take place 12 months after the initial embolization procedure. If the Subject is experiencing ongoing AEs at 12 months, the Subject will be followed until resolution of the AE. The clock will only reset, if during re-treatment the catheter tip detaches in a non-target location and is not resected. Final imaging will be required at this visit. Table 1 describes a list of assessments that will be performed at this visit.

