
PROTOCOL SYNOPSIS	
Sponsor: Micro Therapeutics, Inc. d/b/a ev3 Neurovascular [name]	Protocol Number: NV-APL001 Revision: A, 05-Aug-2014 Product: Apollo™ Onyx™ Delivery Micro Catheter Regulatory Class: Class III Development Phase: Phase IV
Background (cont.): Given the potential side effects of catheter retention and increased procedural risk associated with alternative methods necessary for removing entrapped catheters, a catheter technology that will not leave behind the entire length of a micro catheter is needed. This led to the development of the Apollo™ Onyx™ Delivery Micro Catheter. In the event of catheter retention, using the Apollo™ Onyx™ Delivery Micro Catheter versus any other standard micro catheter represents leaving behind a 1.5-3.0 cm long detachable tip in the Onyx™ cast versus an average 165 cm long catheter in the vasculature.	
Number of Subjects: 161 Subjects with estimated 322 catheter utilizations (~ 2 catheters per Subject)	Number of Study Centers: Up to 25 sites across the United States
Duration of Study: 
• Enrollment: 30 months• Follow-up period: Up to 12 months• Total Study Duration: Up to 42 months	
Primary Composite Endpoint (30 days): Incidence of catheter-related adverse events per Subject: 
• Premature (unintentional) catheter tip detachment with clinical sequelae*• Catheter rupture/break/fracture with clinical sequelae*, and• Retained catheter body in the vasculature	
*Clinical sequelae are defined as all focal neurologic deficits related to lesions within the vascular territory catheterized.	
Acute Secondary Endpoints (30 days): 
1. Rate of premature (unintentional) catheter tip detachment2. Rate of intentional catheter tip detachment3. Rate of migration of the retained catheter tip post embolization4. Incidence of procedure-related adverse events5. Rate of catheter/tip leakage from detachment zone	
Long-Term Secondary Endpoints (12 months): 
1. Incidence of adverse events (AEs)2. Rate of migration of the retained catheter tip post embolization	

[figure not shown]
PROTOCOL SYNOPSIS	
Sponsor: Micro Therapeutics, Inc. d/b/a ev3 Neurovascular [name]	Protocol Number: NV-APL001 Revision: A, 05-Aug-2014 Product: Apollo™ Onyx™ Delivery Micro Catheter Regulatory Class: Class III Development Phase: Phase IV
Clinical Events Committee (CEC):	

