A CEC will be in place for the Study using a minimum of three physicians knowledgeable in the treatment and embolization of brain AVMs. This committee will be responsible for the review and assessment of all study adverse events (AEs) that occur throughout the Study. The CEC is expected to meet each quarter at the minimum.	
Study Population:	
Subjects with a brain AVM that are indicated for AVM embolization with Onyx™ Liquid Embolic System (LES) using the Apollo™ Onyx™ Delivery Micro Catheter.	
Inclusion Criteria:	

1. The Subject or Subject's legally authorized representative has signed and dated an informed consent form.2. The Subject has a confirmed diagnosis of a brain AVM.3. The Subject is clinically and neurologically stable for a minimum of 48 hours prior to embolization.4. The Subject has a life expectancy of at least 1 year.5. The Subject agrees to and is capable of completing all study-required procedures.	
Exclusion Criteria:	

1. Current participation in another investigational drug or device study that evaluates treatments for brain AVMs or other cerebrovascular disease.2. The Subject has a bleeding disorder.3. The Subject is not a candidate for the use of vasodilators.	

PROTOCOL SYNOPSIS	
Sponsor: Micro Therapeutics, Inc. d/b/a ev3 Neurovascular [name]	Protocol Number: NV-APL001
	Revision: A, 05-Aug-2014
	Product: Apollo™ Onyx™ Delivery Micro Catheter
	Regulatory Class: Class III
	Development Phase: Phase IV
Treatment:	
An enrollment screening log will be maintained at each study site. Subjects with brain AVMs enrolled in the study will undergo embolization(s) with Onyx™ 18 LES or Onyx™ 34 LES using the Apollo™ Onyx™ Delivery Micro Catheter. Subjects may undergo multiple procedures over a several week period from the date of the initial study procedure.	
Follow-up:	
All Subjects will complete a 30-day post-embolization visit to assess safety. Once a Subject has completed the study procedures, all ongoing adverse events will be followed until resolution or until event has stabilized.	

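### The 30-day primary endpoint has no stated start point, and timing the 30-day visit of unresected Subjects from the first embolization leaves later staged sessions with less than 30 days of observation

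*Combined protocol and SAP*

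**What the plan says.** The Synopsis and Section 3.1 label the primary composite as a 30-day endpoint without naming the event that starts the 30 days. Section 9.2.4, which defines the analysis, gives neither a window nor a start. Section 9.2.9 says that the primary endpoint is assessed peri-procedurally and plans no imputation.

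The 30-day visit has two anchors. For resected Subjects, Section 5.11.1 says: "Subject who underwent surgical resection will complete a 30-day visit 30 days after surgical resection". For all others: "For Subjects not undergoing surgical resection, the 30 day visit will be performed 30 days after the initial study embolization". Footnote 1 of Table 1 (Section 5.3.1) agrees: "30 day follow-up will occur 30 days after surgical resection, or 30 days after initial embolization if resection is not done". The table allows ±7 days.

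The Synopsis (Treatment) allows staging: "Subjects may undergo multiple procedures over a several week period from the date of the initial study procedure". It gives no maximum interval. Section 5.8 asks for data from each staged session.

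Exit is governed by Section 5.11.1: "Subjects not experiencing an AE and in whom no part of the catheter was retained will complete the study". Section 6 ends adverse event collection at exit. Two groups stay longer. Under Section 5.11.2 and the Synopsis, unresected Subjects with a retained catheter or tip have a 12-month visit. For the other group, Section 5.11.1 says: "Subjects experiencing an AE and in whom no part of the catheter was retained will continue to be followed up until AE resolution".

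The Synopsis (Follow-up) adds a rule for Subjects with retention. It counts 30 days from the initial procedure, even when the retention happens at a later one, and makes no distinction for resected Subjects.

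**The concern.** Two of the three components, tip detachment and catheter rupture, count only when they come with clinical sequelae, and a deficit can appear after the session. If the last session falls well after the first, a visit timed from the first may come too early to see such a deficit, and the exit rule then closes collection.

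Success requires the exact upper bound to fall below 9.6%. An event that is not observed, or not counted, can only lower that bound. The plan also does not say whether an event recorded after day 30 counts, for example in a Subject followed to 12 months, so the count is open to choice at analysis. The interim look can stop the trial for success and is triggered by 80 Subjects reaching the 30-day follow-up. A staged, unresected Subject can therefore count toward the 80 with less than 30 days observed after a later session.

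**Working it through.** **The plan's own figure.** Section 9.1 gives a one-sided 95% exact upper bound of 9.6% for a 5.6% rate in 161 Subjects. 5.6% is 9/161 = 5.59%. The exact bound is the 0.95 quantile of Beta(x + 1, n − x). With x = 9 and n = 161 it is 9.55%, which rounds to 9.6%. The figure reproduces and is not in dispute.

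**Observation time.** Inputs are the visit at 30 days after the first embolization (Section 5.11.1) and the ±7-day window (Table 1).

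- The visit day V runs from 30 − 7 = 23 to 30 + 7 = 37.
- For a Subject who exits at that visit, a session on day d after the first is observed for max(0, V − d) days.
- Even at the latest permitted visit this is below 30 days when 37 − d < 30, that is, when d > 7.

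The documents give no spacing between sessions, so these spacings are assumed:

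| Later session on day | Visit day 23 | Visit day 30 | Visit day 37 |
|---|---|---|---|
| 7 | 16 | 23 | 30 |
| 14 | 9 | 16 | 23 |
| 21 | 2 | 9 | 16 |
| 28 | 0 | 2 | 9 |

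The zero on day 28 means that a day-23 visit would come before the session. That entry applies only if a Subject with a session still pending is allowed to exit.

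**How close the decision boundary is.** Section 9.2.2 judges success on the Full Analysis Set, and the 161 includes 13% attrition: 161 × 0.87 = 140.07, about 140 evaluable Subjects. Both denominators are shown, with the interim level of 96% from Section 9.2.4.

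| Look | Passes | Fails |
|---|---|---|
| 161 Subjects, 95% | 9 events, 9.55% | 10 events, 10.31% |
| About 140 Subjects, 95% | 7 events, 9.19% | 8 events, 10.07% |
| Interim, 80 Subjects, 96% | 2 events, 8.01% | 3 events, 9.79% |

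These rows show the spacing of the boundary. They do not estimate how many events would be missed.

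**Conflicting anchors.** For a resected Subject with a retained catheter or tip, the Synopsis (Follow-up) counts 30 days from the initial procedure, while Section 5.11.1 and Table 1 count from resection. The only rule that resets a clock is in Section 5.11.2. It concerns the 12-month visit, and only an unresected tip detached in a non-target location at re-treatment.

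**The case against.** The strongest reply is Section 9.2.9. If the assessment is peri-procedural, little is lost: detachment, rupture and a retained body are mostly seen at the session. Table 1 also repeats the neurological scales, imaging and adverse event review at discharge or 24 hours after embolization. This stands and narrows the exposure to late-onset sequelae. It does not settle the window, because a peri-procedural assessment and a 30-day label are different definitions.

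The group is also likely to be small. The plan expects 50% to 80% of Subjects to have a retained tip, with about 20% of these not operated on. If one assumes that the same 20% applies to the 20% to 50% with nothing retained, the group is 161 × 0.20 × 0.20 = 6 to 161 × 0.50 × 0.20 = 16 Subjects, before requiring staging. At 5.6% that is about 0.4 to 0.9 primary events of every kind. The plan does not give the unresected share for this group, so this is an illustration, but it argues against a large effect.

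A rupture might itself count as an adverse event and keep the Subject in follow-up, since Section 9.2.4 calls the components adverse events. That is possible but not secure. Section 7 separates a malfunction from an adverse event that results from it, and follow-up lasts only until resolution.

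Resected Subjects are observed to 30 days after surgery, which can only add events. True, but it does not recover events missed in unresected Subjects.

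A reader might infer that Subjects leave the study with sessions still to come, so that events at those sessions are lost. The documents do not establish this. The exit rule states no exception, but Section 5.8 requires data from every staged session, and the flowchart and Figure 3, which might show a repeat-embolization path, are not visible.

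**Conclusion.** The point holds in a limited form, between minor and should-fix. The start of the 30 days is not stated, and the stated visit and exit rules give under 30 days of observation to any session more than 7 days after the first in an unresected Subject with no adverse event and nothing retained. What is mainly exposed is a late deficit in such a Subject. The visit timing rests on the plan's own window; the example spacings are assumed.

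A reader might go further and infer from the one-event margins that the primary conclusion is unsafe. The documents do not support that. They give no session spacing, no number of sessions per Subject and no unresected share for Subjects with nothing retained, so the number of lost events cannot be derived and may be zero. What can be said is that any loss works in one direction, toward meeting the goal, and that the rule for events after day 30 is left open.

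**What to change.** 1. Define the primary-endpoint window in Sections 3.1 and 9.2.4 as running from the first Apollo embolization through 30 days after the last one or, for resected Subjects, through the existing post-resection visit if that is later. Count every recorded event in that window.
2. Time the existing 30-day visit of staged, unresected Subjects to the last embolization.
3. Count a Subject toward the 80-Subject interim only after that visit.
4. Reconcile the Synopsis (Follow-up), Table 1 footnote 1, Section 5.11 and Section 9.2.9 so that they use one anchor and one description of when the endpoint is assessed.

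The cost is wording in the protocol and its statistical section, and a later, not additional, visit for staged, unresected Subjects. The post-resection visit does not change. The downsides are slightly longer follow-up for those Subjects, a slightly later interim and a possibly higher recorded event rate.
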